### **5.4. Concomitant Medications**

Patients must be instructed not to take any additional medications (including over-the-counter products) during the trial without prior consultation with the study physician. All medications taken within 30 days of screening should be noted. If concomitant therapy must be added or changed, the reason and name of the drug/therapy should be recorded.

In general, the use of any concomitant medication/therapies deemed necessary for the care of the patient are allowed, including drugs given prophylactically (e.g. antiemetics) with the following exceptions:

- Any medications which may cause QTc prolongation or induce Torsades de Pointes should not be used (see Appendix F). Dolasetron is contraindicated while on treatment with Panobinostat.
- Any medications that have the potential to alter serum electrolytes (e.g. diuretics) should be monitored very closely for electrolyte abnormalities as these can contribute to the risk of QTc prolongation and vent.
- No other investigational therapy should be given to patients.
- Allopurinol (in subjects at risk for TLS due to high tumor burden) is optional and will be prescribed at the study physician's discretion. These patients may receive allopurinol 300 mg PO BID (Cycle 1 Day -2, Day -1), continuing for 2 days after Cycle 1 Day 1 (total of 4 days), then reduce dose to 300 mg PO QD, continuing through Day 17 of Cycle 1. Allopurinol dose should be adjusted according to the package insert.

- No anticancer agents other than the study medications administered as part of this study protocol should be given to patients. If such agents are required for a patient then the patient must first be withdrawn from the study.
- Leukocyte growth factors (e.g. G-CSF and GM-CSF) are not to be administered prophylactically but may be prescribed by the study physician for severe neutropenia if this is thought to be appropriate.
- Medications known to be substrates of the isoenzyme CYP2D6 should be avoided if possible, as panobinostat can inhibit isoenzyme CYP2D6 at low micromolar ranges (see Appendix G).
- Medications, food, and herbal preparations known to be strong inducers or inhibitors of CYP3A4 should be avoided if possible (see Appendix G).

## **6. DOSE MODIFICATIONS**

The criteria for interruption and resumption of treatment due to toxicity are outlined in the following tables. Dose re-escalation will not be allowed in any patient. All toxicities will be graded utilizing the NCI CTCAE v4.0. If toxicity occurs, the toxicity will be graded, and appropriate supportive care treatment will be administered to decrease the signs and symptoms thereof. If one drug is held, treatment may continue with the other study drug as appropriate. If study medication is held for over 3 weeks due to toxicity, that study medication will be discontinued. Treatment medications will be adjusted with a one level dose-reduction. The dose level criteria in Table 3 should be used to adjust the panobinostat or carfilzomib dose in the event of toxicity. If patients who are on the lowest allowable dose have a toxicity requiring dose reduction, the offending agent should be discontinued. Either or both drugs may be adjusted according to the dose modification tables below.

**Table 4. Panobinostat and Carfilzomib Dose Level Modifications**

Panobinostat PO	Carfilzomib IV
15 mg	15 mg/m 
20 mg	20 mg/m 
30 mg	27 mg/m 
	36 mg/m 
	45 mg/m 
	56 mg/m 

**6.1. Dose Modifications for Hematologic Toxicity**

Panobinostat and carfilzomib have been associated with hematologic toxicity. Blood counts will be measured on Days 1, 8, and 15 of each cycle, and dose modifications will be based on these blood counts. Dose reductions, when necessary, are outlined in Table 5. If toxicity occurs when the patient is already on the lowest acceptable dose, the drug should be discontinued.

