### 5.2.2. Definitions of Dose-Limiting Toxicity (DLT)

For the purpose of determining the MTD (see Section 5.2.3), DLT is defined as any of the following that are determined to be related to study treatment during **Cycle 1**:

- Grade 4 neutropenia (absolute neutrophil count [ANC] <500/ $\mu$ L) for >7 days.
- Febrile neutropenia (ANC <1000/ $\mu$ L with fever >101°F [38.5°C]).
- Grade 3 thrombocytopenia with  $\geq$  Grade 2 bleeding.
- Grade 4 thrombocytopenia (platelets <25,000/ $\mu$ L) > 7 days (patients may receive platelet support/transfusion).
- $\geq$  Grade 2 neuropathy with uncontrolled pain
- $\geq$  Grade 3 non-hematologic drug-related toxicity (excluding alopecia) despite optimal supportive care lasting >72 hours or requiring a dose reduction in the first cycle.
- Patients who are unable to receive 75% of the required doses of both agents secondary to toxicity.

Adverse events will be graded using the National Cancer Institute (NCI) Common Toxicity Terminology Criteria for Adverse Events v4.0 (CTCAE v4.0).

Dose modifications are not permitted during Cycle 1 in any cohort unless the subject experiences a DLT. Subjects in dose level -1 (see Table 2) who develop a DLT during Cycle 1 will be discontinued from the study. Subjects in dose level 1 or higher who experience a DLT during Cycle 1 will have treatment held. The DLT will be counted toward the assessment of the MTD for the given cohort; however, the subject may continue on therapy if the toxicity resolves and dose modifications can be implemented according to the dose modification guidelines in Section 6.0.

Patients who withdraw from the study before receiving 75% of their scheduled Cycle 1 doses due a non-drug related AE (i.e., tumor progression) will be considered inevaluable and will be replaced.

Patients without clinical evidence of progressive disease at the end of the first cycle of study therapy will continue treatment. Patients will be reevaluated for response after completing 2 cycles (8 weeks) of treatment. Patients with objective response or stable disease according the International Myeloma Working Group Uniform Response Criteria (see Appendix C) will continue treatment, with reevaluations until disease progression occurs, unacceptable toxicity develops, or the subject chooses to discontinue study treatment.

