#### **6.4.6. Thrombocytopenia**

Carfilzomib causes thrombocytopenia with platelet nadirs observed between Day 8 and Day 15 of each 28-day cycle with recovery to baseline platelet count by the start of the next cycle. Monitor platelet counts frequently during treatment with carfilzomib. Reduce or withhold dose as appropriate.

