#### **7.3.2. Cycle 1 Day 1**

- Physical examination, including measurement of vital signs (blood pressure, pulse, and respiratory rate) and weight.
- ECOG PS (Appendix A)
- 12-lead ECGs - three ECGs will be obtained 5-10 minutes apart before the patient takes panobinostat and repeated three hours later (x 3) 5-10 minutes apart.
- CBC, 3-part differential and platelets (-3 to Day 1 window allowed)
- CMP (see Section 7.1.) plus magnesium and phosphorus (-3 to Day 1 window allowed)
- Uric acid (-3 to Day 1 window allowed)
- LDH
- PT/PTT/INR (if medically indicated or if patient is receiving warfarin or other anti-coagulant)
- Adverse event evaluation
- Record concomitant medications

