#### **7.3.4. Cycle 1 Day 8 and 15**

- Medical history (Day 15 only)
- Physical examination (Day 15 only)
- ECOG PS (Appendix A)

- Vital signs (blood pressure, weight, pulse, and respiratory rate)
- CBC, 3-part differential and platelets (-3 to Day 1 window allowed)
- CMP (see Section 7.1.) plus magnesium and phosphorus (-3 to Day 1 window allowed)
- Uric acid (-3 to Day 1 window allowed)
- LDH
- PT/PTT/INR (if medically indicated or if patient is receiving warfarin or other anti-coagulant)
- Adverse events assessment
- Record concomitant medication

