**Appendix 5: Schedule of Assessments MM 27**

Procedures	Pre-Treatment	Cycle 1 Cycle = 28 days							Cycle 2 and beyond			Restage Every Cycle (4 weeks)	End of Study Treatment o	Follow-up	
	Baseline A	Day i,j							Day i,j					Off Study Prior to Progression P	After Disease Progression Q
		1	2	5	8	9	15	16	1	8	15				
TESTS & OBSERVATIONS															
Medical history	X						X		X D				X	X	
Physical examination	X	X					X		X D				X	X	
Vital signs, height, weight B	X	X	X	X	X	X	X	X	X	X	X		X	X	
ECOG Performance Status	X	X							X				X	X	
12-lead ECG	X	X G		X G					X H				X	X	
Chest x-ray	X														
MUGA or ECHO	X K														
Adverse event evaluation		X	X	X	X	X	X	X	X	X	X		X	X	
Concomitant medication review	X	X			X		X		X	X	X		X	X	
Survival Status															X
LABORATORY TESTS															
CBC, 3-part differential & platelets	X	X		X		X			X	X	X		X	X	
CMP C plus magnesium & phosphorus	X	X		X		X			X				X	X	
Uric acid & LDH C	X	X		X		X			X S				X S		
PT/INR F	X	X F		X F		X F			X F						
Serum or Urine β-HCG E	X														
DISEASE ASSESSMENTST															
Bone Marrow Aspiration/Biopsy L	X											X L			
Skeletal Survey N	X														
Serum free light chain	X											X M	X M	X M	
Serum immunoglobulin G, A, M	X											X	X	X	
Serum β-2 microglobulin	X														
SPEP & immunofixation	X											X	X	X	
UPEP & immunofixation	X R											X R	X R	X R	

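### If the source table reads as extracted, the Schedule of Assessments puts Cycle 1 laboratory tests on Days 1, 5 and 9 and the protocol text on Days 1, 8 and 15, leaving Day 15 dosing without a scheduled count within 72 hours

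*Combined protocol and SAP*

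**What the plan says.** Section 6.1 ties dose changes for haematologic toxicity to three sampling days: "Blood counts will be measured on Days 1, 8, and 15 of each cycle, and dose modifications will be based on these blood counts". It concerns blood counts only.

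Counts and chemistry for Cycle 1 are set out visit by visit in Section 7.3. Section 7.3.2 (Day 1) lists the CBC, the metabolic profile with magnesium and phosphorus, uric acid and LDH. Section 7.3.4, headed "Cycle 1 Day 8 and 15", lists the same tests. Both add coagulation tests where indicated. Section 7.3.3 (Day 5) lists ECGs and vital signs but no laboratory tests. No text section places laboratory tests on Day 9.

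The Schedule of Assessments (Appendix E, headed Appendix 5 in the body) has Cycle 1 columns for Days 1, 2, 5, 8, 9, 15 and 16. As extracted, the row "CBC, 3-part differential & platelets" and the three rows below it (metabolic profile; uric acid and LDH; PT/INR) carry Cycle 1 marks under Days 1, 5 and 9. Days 8 and 15 are blank.

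Section 5 schedules panobinostat on Days 1, 3, 5, 15, 17 and 19, and carfilzomib on Days 1, 2, 8, 9, 15 and 16. Section 5.2.2 counts Grade 4 neutropenia and Grade 4 thrombocytopenia as DLTs when they last more than 7 days in Cycle 1.

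**The concern.** Section 7 sends sites to the Schedule of Assessments for the visit plan, so a site may well work from the table. The table would give it no scheduled count or chemistry near Day 15, the first day since Day 1 on which both drugs are given together and one of the three days on which Section 6.1 bases dose modification. Section 5.1.1.1 also makes panobinostat dosing depend on the most recent electrolyte values. Under the table, the most recent scheduled values on Day 15 would be those of Day 9.

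The second stake is measurement of the Phase I endpoint. Two DLT criteria are defined by how long a laboratory abnormality lasts, so they can be recorded only if a count falls inside the episode. Section 5.2.1 acts on very small numbers: 0 of 3 escalates, 1 of 3 expands the cohort to 6, and 2 of 6 means the maximum tolerated dose has been exceeded. One unrecorded event can change the action.

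**Working it through.** The plan states no figure on this point, so there is none to reproduce. The check is a comparison of days, followed by a count of what each schedule would miss.

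**1. Days side by side (Cycle 1)**

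| Test | Protocol text | Schedule of Assessments, as extracted |
|---|---|---|
| CBC | 1 (7.3.2), 8 and 15 (7.3.4); also 6.1 | 1, 5, 9 |
| Metabolic profile, Mg, P | 1 (7.3.2), 8 and 15 (7.3.4) | 1, 5, 9 |
| Uric acid and LDH | 1 (7.3.2), 8 and 15 (7.3.4) | 1, 5, 9 |
| PT/INR, if indicated | 1 (7.3.2), 8 and 15 (7.3.4) | 1, 5, 9 |

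**2. Is the table aligned?** Each row checked has 15 cells for the 15 columns. ECGs fall on Days 1 and 5, medical history on Day 15, concomitant medication on Days 1, 8 and 15, and the Cycle 2 CBC on Days 1, 8 and 15, all as in the text. Only the laboratory rows differ: the last two Cycle 1 marks sit one column to the left of Days 8 and 15.

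**3. Does the window cover the dosing days?** Footnote C allows laboratory samples within 72 hours. It is attached to the chemistry rows; applying it to the CBC as well favours the table.
- Day 8: 8 − 5 = 3 days = 72 hours, so the Day 5 sample can serve.
- Day 15: 15 − 9 = 6 days = 144 hours, so the Day 9 sample cannot.

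**4. Gaps between scheduled counts**, taking Cycle 2 Day 1 as study day 29:
- Table (1, 5, 9, 29): 4, 4 and 20 days.
- Text (1, 8, 15, 29): 7, 7 and 14 days.

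**5. Episodes that no scheduled count would meet.** Take an episode of L days lying wholly within Days 2 to 28. It has 27 − L + 1 = 28 − L possible start days. It fits unseen between counts on days a and b for max(0, b − a − L) start days. For L ≥ 8 only the last gap contributes.

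| Length L | Start days (28 − L) | Missed, table (20 − L) | Missed, text (14 − L) |
|---|---|---|---|
| 8 | 20 | 12 | 6 |
| 10 | 18 | 10 | 4 |
| 14 | 14 | 6 | 0 |

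If the Cycle 2 Day 1 sample is drawn 3 days early, as the text allows, the last gaps become 17 and 11 days, and the 8-day figures become 17 − 8 = 9 and 11 − 8 = 3 of 20.

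These are counts of start days, not probabilities; the documents give no distribution of onset. An episode that is met is not yet shown to last more than 7 days. Days 8 and 15 are only 7 days apart, so the text schedule also depends on repeat counts triggered by an abnormal result.

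**The case against.** **The table may be misread.** The text examined is a machine reading of the PDF. The four affected rows are adjacent, and the same one-column shift would explain all of them. The correctly placed Cycle 1 rows belong to a different block of the table, and correct Cycle 2 marks do not rule out a shift confined to Cycle 1. This stands, and it is why the point is conditional. Against it, the rows have their full cell count. The table also departs from the text elsewhere: Section 7.3.4 lists ECOG status on Days 8 and 15, which the table leaves blank.

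**The text is explicit.** Sections 6.1 and 7.3.4 are clear, and nothing gives the appendix precedence. A site that reads the text would sample on Day 15. This also stands: the consequence applies to a site using the table alone.

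**Toxicity would not go unseen.** A reader might infer that such a site could not see haematologic DLTs, or would have no count or electrolyte result before Day 15. The documents do not support either reading. Samples would exist from Days 1, 5 and 9. Day 9 lies within the period that Section 6.4.6 gives for carfilzomib, "platelet nadirs observed between Day 8 and Day 15 of each 28-day cycle", and that section asks for frequent platelet monitoring. Section 5 requires a DLT assessment before treatment at each Cycle 1 visit. Table 5 has laboratory tests repeated weekly until recovery. Febrile neutropenia and bleeding have clinical signs. Section 5.1.2.1 strongly encourages chemistry before each carfilzomib dose in Cycles 1 and 2.

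**Much of the late gap is common to both schedules.** The text itself leaves 14 days after Day 15. Only the excess, 20 against 14 days and 12 against 6 start days, belongs to the discrepancy.

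**Conclusion.** Provided the source table matches the extracted one, the protocol holds two incompatible Cycle 1 laboratory schedules. A site following the table alone would give both drugs on Day 15 with no scheduled sample in the preceding 72 hours, although Section 6.1 bases dose modification on that day's count. Detection of Grade 4 cytopenias lasting more than 7 days would be weakened, not abolished: an 8-day episode is missed for 12 of 20 start days instead of 6 of 20.

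These figures assume scheduled counts only, on their nominal days, and an episode that begins and ends within Days 2 to 28.

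A reader might go further and infer that DLT counts are biased towards tolerability, or that the absence of DLTs reported in Section 5 for the first four dose levels is unreliable. The documents do not show which schedule sites followed or how often silent episodes fall in the gap, so neither inference is supported.

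**What to change.** Check the Cycle 1 columns of the Schedule of Assessments in the source document. If the laboratory rows read Days 1, 8 and 15 there, the point falls away.

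If they read Days 1, 5 and 9, reconcile Section 6.1, Sections 7.3.2 to 7.3.4 and Appendix E so that all give one Cycle 1 laboratory schedule, and so that the counts on which Section 6.1 bases dose modification are the counts the schedule calls for. Which days are right is for the sponsor and investigators to settle; this point requires only agreement between the passages.

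The cost is an editorial amendment. Both schedules have three Cycle 1 sampling days, and all the days concerned are already visit columns in the table, so choosing either adds no visit and no blood draw.

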**Table 5. Panobinostat and Carfilzomib Dose Adjustments for Hematologic Toxicities**

AE Term and Description	Dose Modification	
	Panobinostat	Carfilzomib
THROMBOCYTOPENIA		
Grade 1 or 2	Maintain dosing; monitor as clinically indicated.	Maintain dosing; monitor as clinically indicated.
Grade 3 (25 - <50 x 10  /L)	
 
1. Interrupt study treatment until toxicity reduced to ≤ grade 2a.
 
2. Restart treatment with a 1 level dose-reduction (Table 3).
 
	
 
1. Interrupt study treatment until toxicity reduced to ≤ grade 2a.
 
2. If improves in ≤ 7 days, maintain same dose, if > 7 days reduce dose 1 level.
 

Grade 4 (<25 x 10  /L)	
 
1. Interrupt study treatment until toxicity reduced to ≤ grade 2a.
 
2. Restart treatment with a 1 level dose-reduction.
 
	
 
1. Interrupt study treatment until toxicity reduced to ≤ grade 2a.
 
2. Restart treatment with a 1 level dose-reduction.
 

Recurrent Grade 3/4 Event After Initial Dose Reduction	
 
1. Interrupt study treatment until toxicity reduced to ≤ grade 2a.
 
2. Restart treatment with a second 1 level dose-reduction.
 
	
 
1. Interrupt study treatment until toxicity reduced to ≤ grade 2a.
 
2. Restart treatment with a second 1 level dose-reduction.
 

Recurrent Grade 3/4 Event After 2 Dose Reductions	Discontinue	Discontinue

**Table 5. Panobinostat and Carfilzomib Dose Adjustments for Hematologic Toxicities (continuation)**

AE Term and Description	Dose Modification	
	Panobinostat	Carfilzomib
NEUTROPENIA		
Grade 1 or 2	Maintain dosing; monitor as clinically indicated.	Maintain dosing; monitor as clinically indicated.
Grade 3 ( $0.5 \times 10^9/L \leq ANC < 1.0 \times 10^9/L$ )	
 
1. Interrupt study treatment until toxicity reduced to <math>\leq</math> grade 2a.
 
2. Restart treatment with a 1 level dose-reduction (Table 3).
 
	
 
1. Interrupt study treatment until toxicity reduced to <math>\leq</math> grade 2a.
 
2. If improves in <math>\leq</math> 7 days, maintain same dose, if <math>>7</math> days reduce dose 1 level.
 

Grade 4 ( $ANC < 0.5 \times 10^9/L$ )	
 
1. Interrupt study treatment until toxicity reduced to <math>\leq</math> grade 2a.
 
2. Restart treatment with a 1 level dose-reduction.
 
	
 
1. Interrupt study treatment until toxicity reduced to <math>\leq</math> grade 2a.
 
2. Restart treatment with a 1 level dose-reduction.
 

Recurrent Grade 3/4 Event After Initial Dose Reduction	
 
1. Interrupt study treatment until toxicity reduced to <math>\leq</math> grade 2a.
 
2. Restart treatment with a 1 level dose-reduction.
 
	
 
1. Interrupt study treatment until toxicity reduced to <math>\leq</math> grade 2a.
 
2. Restart treatment with a 1 level dose-reduction.
 

Recurrent Grade 3/4 Event After 2 Dose Reductions	Discontinue	Interrupt until toxicity $\leq$ grade 2 a and restart treatment with a 1 level dose-reduction if possible, or discontinue.
FEBRILE NEUTROPENIA		
Grade 3 ANC $< 1.0 \times 10^9/L$ , fever $\geq 38.5^\circ C$	
 
1. Interrupt study treatment until ANC recovery to <math>\leq</math> grade 2a (<math>ANC \geq 1.0 \times 10^9/L</math>) and resolution of fever <math>< 38.5^\circ C</math>.
 
2. Restart treatment with a 1 level dose-reduction.
 
	
 
1. Interrupt study treatment until ANC recovery to <math>\leq</math> grade 2a (<math>ANC \geq 1.0 \times 10^9/L</math>) and resolution of fever <math>< 38.5^\circ C</math>.
 
2. Restart treatment with a 1 level dose-reduction.
 

Grade 4 ANC $< 1.0 \times 10^9/L$ , fever $\geq 38.5^\circ C$ and life-threatening consequences	Discontinue	
 
1. Interrupt study treatment until ANC recovery to <math>\leq</math> grade 2a (<math>ANC \geq 1.0 \times 10^9/L</math>) and resolution of fever <math>< 38.5^\circ C</math> and any complications.
 
2. Restart treatment with a 1 level dose-reduction.
 

a Repeat labs weekly until recovery.

The criteria for adjusting the dose of panobinostat in the event of non-hematologic toxicities are detailed in Table 6.

**Table 6. Panobinostat Dose Adjustments for Non-Hematologic Toxicities**

AE Term and Description	Panobinostat Dose Modification
RENAL	
Serum Creatinine	
Serum creatinine < 2 x ULN	Maintain dosing.
Serum creatinine 2-3 X ULN	
 
1. Interrupt panobinostat until toxicity resolved to ≤ 1.5 X ULN.
 
2. Restart treatment with a 1 level dose-reduction (Table 3).
 

Serum creatinine (>3 X ULN) Grade 3 or 4	Discontinue panobinostat
Recurrent Event After Initial Dose Reduction	
 
1. Interrupt panobinostat until toxicity ≤ 1.5 X ULN.
 
2. Restart treatment with a second 1 level dose-reduction.
 

Recurrent Event After 2 Dose Reductions	Discontinue panobinostat
HEPATIC	
Total Bilirubin	
Total bilirubin < 2 x ULN	Maintain dosing.
Total bilirubin 2-3 X ULN	
 
1. Interrupt panobinostat until toxicity resolved to ≤ 1.5 X ULN.
 
2. Restart treatment with a 1 level dose-reduction (Table 3).
 

Total bilirubin (>3 X ULN) Grade 3 or 4	Discontinue panobinostat
Recurrent Event After Initial Dose Reduction	
 
1. Interrupt panobinostat until toxicity ≤ 1.5 X ULN.
 
2. Restart treatment with a second 1 level dose-reduction.
 

Recurrent Event After 2 Dose Reductions	Discontinue panobinostat
AST/SGOT, ALT/SGPT	
AST/SGOT, ALT/SGPT ≤5 x ULN (Grade 1 or 2)	Maintain dosing.
AST/SGOT, ALT/SGPT >5 - 10 x ULN	
 
1. Interrupt panobinostat until toxicity resolved to ≤ grade 1 (or baseline).
 
2. Restart treatment with a 1 level dose-reduction (Table 3).
 

Total bilirubin (>3 X ULN) Grade 3 or 4	Discontinue panobinostat
Recurrent Event After Initial Dose Reduction	
 
1. Interrupt panobinostat until toxicity resolved to ≤ grade 1 (or baseline).
 
2. Restart treatment with a second 1 level dose-reduction.
 

Recurrent Event After 2 Dose Reductions	Discontinue panobinostat

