**Table 6. Panobinostat Dose Adjustments for Non-Hematologic Toxicities (continuation)**

AE Term and Description	Panobinostat Dose Modification
GASTROINTESTINAL	
Diarrhea	
Grade 1	Maintain dosing.
Grade 2 or Grade 3  (Despite anti-diarrheal therapy)	1. Interrupt panobinostat until toxicity resolved to ≤ grade 1. 2. Restart treatment with a 1 level dose-reduction (Table 3).
Grade 4	Discontinue panobinostat
Recurrent Event After Initial Dose Reduction	1. Interrupt panobinostat until toxicity resolved to ≤ grade 1. 2. Restart treatment with a second 1 level dose-reduction.
Recurrent Event After 2 Dose Reductions	Discontinue panobinostat
Vomiting	
Grade 1	Maintain dosing.
Grade 2 or Grade 3  (Despite anti-nausea therapy)	1. Interrupt panobinostat until toxicity resolved to ≤ grade 1. 2. Restart treatment with a 1 level dose-reduction (Table 3).
Grade 4	Discontinue panobinostat
Recurrent Event After Initial Dose Reduction	1. Interrupt panobinostat until toxicity resolved to ≤ grade 1. 2. Restart treatment with a second 1 level dose-reduction.
Recurrent Event After 2 Dose Reductions	Discontinue panobinostat
Fatigue	
Grade 4	1. Interrupt panobinostat until toxicity resolved to ≤ grade 2 or baseline. 2. If resolved in 7 days after interruption of panobinostat, then restart panobinostat at an unchanged dose level. 3. If resolved in more than 7 days after interruption of panobinostat, then restart panobinostat with a 1 level dose-reduction.
Other Non-Hematologic Toxicity	
Grade 3	1. Interrupt panobinostat until toxicity resolved to ≤ grade 1 or baseline. 2. Restart treatment with a 1 level dose-reduction (Table 3).
Grade 4	Discontinue panobinostat
Recurrent Event After Initial Dose Reduction	1. Interrupt panobinostat until toxicity resolved to ≤ grade 1. 2. Restart treatment with a second 1 level dose-reduction.
Recurrent Event After 2 Dose Reductions	Discontinue panobinostat

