**Table 6. Panobinostat Dose Adjustments for Non-Hematologic Toxicities (continuation)**

Each patient is allowed a maximum of 2 dose reductions (Table 3). No patient will receive less than 15 mg three times weekly. If toxicity recurs at this dose level, panobinostat will be discontinued.
Patients with grade 4 adverse event should be discontinued from further treatment with study drug.
* Common Terminology Criteria for Adverse Events (CTCAE Version 4.0)

 Patients should be instructed to contact their physician at the onset of diarrhea. Each patient should be instructed to have loperamide readily available and to begin treatment for diarrhea at the first episode of poorly formed or loose stools or the earliest onset of bowel movements more frequent than normally expected for the patient. Loperamide 4 mg should be taken at the first loose stool or more frequent than usual bowel movements, followed by 2 mg as needed, no more frequently than every 4 hours not to exceed a total of 16 mg in 24 hours. Patients with diarrhea grade 2 despite this loperamide regimen should interrupt treatment with panobinostat as described in the table. If the above regimen is inadequate then additional evaluation and treatment should be pursued as medically indicated. Premedication with loperamide is not recommended.
 
The use of drugs with laxative properties should be avoided because of the potential for exacerbation of diarrhea. Patients should be advised to contact their physician to discuss any laxative use. Patients should be instructed to contact their physician at the onset of diarrhea.
 
If severe diarrhea (grade 3 and 4) happens, patient should be admitted into the hospital. Replace IV fluids and electrolytes as appropriate. Treatment should follow institutional standard of care or local guidelines.
 
If patient has two grade 3 diarrhea events or vomiting episodes with or without prophylaxis medications, the patient may be discontinued from study drug rather than attempting dose reductions at the discretion of the investigator.

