### **6.3. Carfilzomib Dose Modifications for Non-Hematologic Toxicities**

Treatment with carfilzomib and panobinostat should be held for  $\geq$  grade 3 events until resolved to  $\leq$  grade 1 or return to baseline. If the adverse event was not treatment-related, or was attributable to panobinostat, subsequent treatment with carfilzomib may be resumed at full dose after resolution to  $\leq$  grade 1 or return to baseline.

If the event was carfilzomib-related, subsequent treatment with carfilzomib will resume at one level dose reduction (see Table 3). If toxicity continues or recurs, a 2nd carfilzomib dose reduction is permitted unless the patient is already receiving the lowest dose level shown in Table 3. If toxicity continues, the patient should be discontinued from treatment.

If there is no resolution of carfilzomib-related toxicity after 2 weeks of withholding carfilzomib (up to 3 weeks for infection treatment), carfilzomib will be discontinued.

Specific carfilzomib-associated non-hematologic toxicities are addressed in Table 7.

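### Table 6's AST/ALT block stops panobinostat on bilirubin, so a first AST/ALT above 10 x ULN but below grade 4 has no clear action after recovery

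*Combined protocol and SAP*

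**What the plan says.** Table 6 (panobinostat, non-hematologic toxicity) has three renal and hepatic laboratory blocks: serum creatinine, total bilirubin, and AST/ALT.

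- **Creatinine and bilirubin.** Each block has a maintain row, an interrupt-and-reduce row for 2-3 x ULN, and a discontinue row on its own analyte. For creatinine the discontinue row is "Serum creatinine (>3 X ULN) Grade 3 or 4".
- **AST/ALT.** Dosing is maintained up to 5 x ULN, which the table labels grade 1 or 2. The next row is "AST/SGOT, ALT/SGPT >5 - 10 x ULN", with interruption and a restart one level lower. The discontinue row then has the trigger "Total bilirubin (>3 X ULN) Grade 3 or 4". Two recurrent-event rows follow.

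Other text that bears on a high AST/ALT:

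- The block headed "Other Non-Hematologic Toxicity" restarts one level lower after grade 3 and stops at grade 4.
- A note under Table 6 says "Patients with grade 4 adverse event should be discontinued from further treatment with study drug". Another note caps reductions at two and sets a floor of 15 mg.
- Section 6.3 begins "Treatment with carfilzomib and panobinostat should be held for" events of grade 3 or higher. The rules for resuming and reducing that follow are for carfilzomib.
- Section 6 says "If study medication is held for over 3 weeks due to toxicity, that study medication will be discontinued". It also names a one-level reduction as the general adjustment and refers to the tables for the criteria.

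**The concern.** A stopping row in a safety table that sites act on tests the wrong analyte. AST or ALT can never trigger the first-event stop in its own block, and the row adds nothing to the identical bilirubin row above it.

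Patients are not dosed while the value is high, because the drug is held under any reading. The difference comes after recovery. Two sites facing the same laboratory value could do opposite things: end panobinostat for good, or give it again at a lower dose. Panobinostat is given here with carfilzomib, for which Section 6.4.7 reports transaminase elevations and fatal hepatic failure. Section 5.2.2 also relies on the Section 6 guidelines to decide whether a patient may continue after a Cycle 1 DLT.

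**Working it through.** The plan states no figure to reproduce on this point. The check maps each AST/ALT range to the rule that governs it, then measures what is left.

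**Step 1. Coverage of a first AST/ALT event, with bilirubin at or below 3 x ULN**

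| AST/ALT | Governing text | Action on panobinostat |
|---|---|---|
| Up to 5 x ULN | AST/ALT block, first row | Maintain |
| >5 to 10 x ULN | AST/ALT block, second row | Interrupt, restart one level lower |
| >10 x ULN, below grade 4 | No row in the block | Held (Section 6.3); action after recovery not settled |
| Grade 4 | Note under Table 6; grade 4 row of the catch-all block | Discontinue |

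If recovery takes more than 3 weeks, Section 6 ends the drug. The open case is therefore the third row with recovery within 3 weeks.

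**Step 2. Two readings of the open case**

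- *Stop.* The creatinine and bilirubin blocks both discontinue directly above their restart band. By analogy, the AST/ALT row was meant to discontinue above 10 x ULN.
- *Restart lower.* The grade 3 row of the catch-all block interrupts and restarts one level lower. That is essentially the action already given for >5 to 10 x ULN, so under this reading the 10 x ULN cut separates nothing.

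The structure favors the stop reading, but no sentence states it.

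**Step 3. Is the row a text-extraction fault or a deliberate combined liver rule?**

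An extraction fault is unlikely, though it cannot be fully excluded. The row is complete and its action cell is intact. The recurrent-event rows below it use the AST/ALT recovery target (grade 1 or baseline), not the bilirubin target (1.5 x ULN). That fits a trigger cell copied in the source. A combined rule is also unlikely, because the row names no AST/ALT value and does not join two conditions. Even as a combined rule, it would leave an isolated AST/ALT rise above 10 x ULN without a row.

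**Step 4. Difference in exposure between the readings**

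Table 4 gives panobinostat levels of 30, 20 and 15 mg, and at most two reductions are allowed.

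- Start at 30 mg (dose levels 4 and 5): 20 mg, then 15 mg, so 2 lower levels are open.
- Start at 20 mg (dose levels 1 to 3 and 6): 15 mg, so 1 lower level is open.
- Stop reading: 0 lower levels in either case.

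**Step 5. Width of the open range**

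Section 6 names CTCAE v4.0 but the documents do not print the AST/ALT cut for grade 4, so it is assumed here. Width = assumed grade 4 start − 10:

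| Assumed grade 4 start (x ULN) | Width of open range (x ULN) |
|---|---|
| 10 | 10 − 10 = 0 |
| 12 | 12 − 10 = 2 |
| 15 | 15 − 10 = 5 |
| 20 | 20 − 10 = 10 |

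For comparison, the restart band is 10 − 5 = 5 x ULN wide. At a start of 10 x ULN the gap closes and only the wrong trigger remains. Below 10 x ULN, the restart band itself would conflict with the grade 4 stop.

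**The case against.** The strongest reply accepts the duplicated row and argues that little follows from it.

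- **The written text gives an answer.** Section 6 names a one-level reduction as the general adjustment, and the catch-all grade 3 row says the same. The stop reading has only analogy behind it. This has some force, but it does not settle the matter: AST/ALT has its own block, so a row for other toxicities does not clearly reach it. The general sentence sits beside many explicit discontinue rows, and Section 6 leaves the criteria to the tables.
- **The analogy is imperfect.** The creatinine and bilirubin blocks stop at grade 3 or 4, while the AST/ALT block already allows a restart above 5 x ULN, which is at least grade 3 by its own labels. The diarrhea and vomiting blocks also restart at grade 3 and stop at grade 4. This stands as a reason not to treat the stop as established. It does not explain why the table cuts at 10 x ULN.
- **Section 3.3 offers another route to a stop**, for intolerable toxicity or drug-related laboratory abnormalities. It does, but by judgment, so sites can still differ.
- **The consequence is narrow.** Grade 4 stops, grade 3 is held, long holds end the drug, and reductions are capped. No endpoint, sample size or error rate changes. All of this stands and limits the size of the point.

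**Conclusion.** The concern holds. The AST/ALT stopping row carries the wrong trigger, and the plan does not decide between a permanent stop and a restart one level lower after a first AST/ALT above 10 x ULN, below grade 4, that recovers within 3 weeks.

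Confidence is high for the wrong trigger. That the intended threshold was 10 x ULN is an inference from the neighboring blocks. The width of the gap rests on the assumed grade 4 cut, and the documents do not say how often such values occur. The affected range is narrow, but this is an operative safety rule, and the table needs correction whichever grade 4 cut applies.

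**What to change.** In the AST/ALT block of Table 6, replace the bilirubin trigger in the stopping row with AST/SGOT or ALT/SGPT above 10 x ULN, and keep the discontinue action. Add one line saying that the AST/ALT block takes precedence over the catch-all rows for other non-hematologic toxicity. The sponsor should confirm the threshold first, because it is inferred. The bilirubin block needs no change.

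The cost is one table cell and one line in the next amendment, with a notice to sites. No new test is needed, since AST and ALT are already in the metabolic profile of Section 7.1. The downside is that a few patients who might have been rechallenged at a lower dose would stop panobinostat.
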